10.3.6 Reporting of AEs, SAEs, and Other Reportable Safety Events to the Sponsor

AE, SAE, and other reportable safety event reporting to Sponsor via electronic data collection tool

- The primary mechanism for reporting to the Sponsor will be the EDC tool.
 - Electronic reporting procedures can be found in the EDC data entry guidelines (or equivalent).
 - If the electronic system is unavailable for more than 24 hours, then the site will use the paper AE Reporting form.
 - Reference Section 8.4.1 for reporting time requirements.
- The site will enter the SAE data into the electronic system as soon as it becomes available.
- After the study is completed at a given site, the EDC tool will be taken off-line to prevent the entry of new data or changes to existing data.
- If a site receives a report of a new SAE from a study participant or receives updated data on a previously reported SAE after the EDC tool has been taken off-line, then the site can report this information on a paper SAE form or by telephone (see next section).
- Contacts for SAE reporting can be found in the Investigator Study File Binder (or equivalent).

SAE reporting to the Sponsor via paper CRF

- If the EDC tool is not operational, facsimile transmission or secure e-mail of the SAE paper CRF is the preferred method to transmit this information to the Sponsor.
- In rare circumstances and in the absence of facsimile equipment, notification by telephone is acceptable with a copy of the SAE data collection tool sent by overnight mail or courier service.
- Initial notification via telephone does not replace the need for the investigator to complete and sign the SAE CRF pages within the designated reporting time frames.
- Contacts and instructions for SAE reporting and paper reporting procedures can be found in the Investigator Study File Binder (or equivalent).

10.4 Appendix 4: Device Events, Adverse Device Events, and Medical Device Incidents: Definitions, Collection, and Documentation

Not applicable

10.5 Appendix 5: Contraceptive Guidance

10.5.1 Definitions

Women of Childbearing Potential (WOCBP)

A woman is considered fertile following menarche and until becoming postmenopausal unless permanently sterile (see below):

If fertility is unclear (eg, amenorrhea in adolescents or athletes) and a menstrual cycle cannot be confirmed before first dose of study intervention, additional evaluation should be considered.

Women in the following categories are not considered WOCBP:

- Premenarchal
- Premenopausal female with 1 of the following:
 - Documented hysterectomy
 - Documented bilateral salpingectomy
 - Documented bilateral oophorectomy

For individuals with permanent infertility due to an alternate medical cause other than the above (eg, Mullerian agenesis, androgen insensitivity), investigator discretion should be applied to determining study entry.

Note: Documentation can come from the site personnel's review of the participant's medical records, medical examination, or medical history interview.

- Postmenopausal female
 - A postmenopausal state is defined as no menses for 12 months without an alternative medical cause.
 - A high FSH level in the postmenopausal range may be used to confirm a postmenopausal state in women not using hormonal contraception or HRT. However, in the absence of 12 months of amenorrhea, confirmation with two FSH measurements in the postmenopausal range is required.
 - Females on HRT and whose menopausal status is in doubt will be required to use one of the nonhormonal highly effective contraception methods if they wish to continue their HRT during the study. Otherwise, they must discontinue HRT to allow confirmation of postmenopausal status before study enrollment.

10.5.2 Contraception Requirements

Contraceptives allowed during the study include^a:
Highly Effective Contraceptive Methods That Have Low User Dependency Failure rate of <1% per year when used consistently and correctly.

• Progestogen-only subdermal contraceptive implant^{b,c}• IUS^c• Non-hormonal IUD• Bilateral tubal occlusion

• Azoospermic partner (vasectomized or secondary to medical cause) This is a highly effective contraception method provided that the partner is the sole male sexual partner of the WOCBP and the absence of sperm has been confirmed. If not, an additional highly effective method of contraception should be used. A spermatogenesis cycle is approximately 90 days. Note: Documentation of azoospermia can come from the site personnel's review of the participant's medical records, medical examination, or medical history interview.
Sexual Abstinence 
• Sexual abstinence is considered a highly effective method only if defined as refraining from heterosexual intercourse during the entire period of risk associated with the study intervention. The reliability of sexual abstinence needs to be evaluated in relation to the duration of the study and the preferred and usual lifestyle of the participant.

^a Contraceptive use by men or women should be consistent with local regulations regarding the use of contraceptive methods for participants of clinical studies.
 
^b If locally required, in accordance with CTFG guidelines, acceptable contraceptive implants are limited to those which inhibit ovulation.
 
^c IUS is a progestin-releasing IUD.
 
Note: The following are not acceptable methods of contraception:
 
- Periodic abstinence (calendar, symptothermal, post-ovulation methods), withdrawal (coitus interruptus), spermicides only, and LAM.- Male condom with cap, diaphragm, or sponge with spermicide.- Male and female condom should not be used together (due to risk of failure with friction).

10.6 Appendix 6: Collection and Management of Specimens for Future Biomedical Research

Not applicable

10.7 Appendix 7: Country-specific Requirements

10.7.1 Sweden

If serum creatinine is greater than the maximum serum creatinine for age and gender as shown in the table below, then creatinine clearance (or radioisotope glomerular filtration rate [eGFR]) must be >70 mL/min/1.73 m².

If applicable, the 2009 Schwartz equation must be used to estimate GFR for participants aged <18 years (ie, $eGFR = 36.5 \times \text{height [cm]} / \text{plasma creatinine } [\mu\text{mol/L}]$) [Schwartz, G. J., et al 2009].

Age	Maximum Serum Creatinine (mg/dL)		Maximum Serum Creatinine ($\mu\text{mol/L}$)	
	Male	Female	Male	Female
2 to <6 years	0.8	0.8	70.72	70.72
6 to <10 years	1	1	88.4	88.4
10 to <13 years	1.2	1.2	106.08	106.08
13 to <16 years	1.5	1.4	132.6	123.76
≥ 16 years	1.7	1.4	150.28	123.76

10.7.2 Czech Republic

Section 5.2 Exclusion Criteria

11. Known to be HIV positive. Note: HIV testing is required at screening.

12. Has known active viral hepatitis B virus (eg, HBsAg reactive) or Hepatitis C virus (eg, HCV RNA [qualitative] is detected) infection. Note: Testing for hepatitis B or hepatitis C is required at screening.

Section 8.11.1 Screening

Laboratory tests are to be performed within 7 days prior to the first dose of study intervention. Exceptions are hepatitis testing and HIV testing which may be performed up to 28 days prior to the first dose of study intervention.

10.7.3 Italy

- eGFR for pediatric subjects under 18 years old should be calculated exclusively with the Bedside Schwartz equation for participants in Italy.
- The blood volume to be taken from a pediatric participant must not exceed the allowable maximum outlined in “Ethical Considerations for Clinical Trials on Medicinal Products Conducted With Minors” (3% of the total blood volume over a 4-week period or 1% at any single time)[European Commission 2017]. If the blood volume is insufficient to conduct all planned analyses, safety laboratory tests should be prioritized for participants in Italy.

10.8 Appendix 8: Response Assessment in Neuro-Oncology (RANO) Response Criteria

For HGG, treatment response assessment will be based on the RANO criteria [Wen PY, Macdonald DR, Reardon DA, Cloughesy TF, Sorensen AG, 2010], using a combination of clinical and imaging data. At baseline, tumor burden is documented by selection of lesions that will be followed quantitatively (target lesions) and qualitatively (nontarget). At each visit afterward, imaging assessment consists of evaluating target and nontarget lesions, searching for new lesions, and review of the abnormalities on Fluid Attenuated Inversion Recovery (T2/FLAIR) images. These assessments are combined into a radiographic response, which is then combined with clinical performance status and steroid dose information to determine the overall response for each visit. Endpoint information, such as the best overall response, is determined from the sequence of visit responses as described in the SAP.

Scan acquisition

Imaging will be acquired using the standardized Brain Tumor Imaging Protocol [Ellingson, B. M., Bendszus, M., et al 2015]. It will include pre- and post-contrast T1-weighted MRI, as well as T2/FLAIR and diffusion-weighted imaging. The same technique should be used at baseline and all follow-up scans.

Lesion measurements

Lesions should be measured on T1 weighted post-gadolinium images, in the axial plane. The 2 maximal perpendicular outer diameters of each enhancing lesion should be measured. In lesions that have cystic components, areas of necrosis, or surgical cavities, every effort should be made to measure only the solid portions of the lesion, excluding the non-solid components. In particular, if a patient has a surgical cavity surrounded by enhancement, the cavity should not be included in the measurement. If there is nodular enhancement associated with the cavity, the nodular component alone should be measured.

Baseline tumor documentation

Reviewers will document baseline tumor on post-contrast T1-weighted and T2/FLAIR images. They first identify all lesions, determine whether they are measurable (can be measured), and from these choose target lesions (will be measured throughout the trial). To be considered measurable, a lesion has to show enhancement, have 2 perpendicular diameters ≥ 10 mm, and be suitable for reproducible repeated measurements. Enhancing non-measurable lesions include all other enhancement that is strongly believed to represent tumor, but that does not meet the requirements above. Up to 5 lesions can be selected as target. Selected target lesions are measured, and the sum of products of diameters (SPD) calculated. Enhancing nontarget lesions are identified by location only. Because T2/FLAIR abnormalities are typically more diffuse than tumor enhancement, the T2/FLAIR images will be used for comparison when evaluating later visits, without identification of discrete lesions.

Radiographic response assessment

Target lesion response is determined by the change in the sum of diameters from baseline and from nadir (smallest measurement seen until the visit being evaluated) (Table 8).

Table 8 Target Lesion Response

Response	Definition
Complete Response (CR)	All target lesions have completely disappeared.
Partial Response (PR)	SPD decreased by $\geq 50\%$ from baseline value.
Stable Disease (SD)	SPD $< 50\%$ decreased from baseline, but $< 25\%$ increased from nadir.
Progressive Disease (PD)	SPD increased by $\geq 25\%$ from nadir value.
Non-evaluable (NE)	The sum of diameters cannot be meaningfully evaluated (for example, because of technical factors such as scan quality that obscure one or more target lesions).

Nontarget lesion response is determined by visual inspection of enhancing nontarget lesions collectively and classification into a response category (Table 9).

Table 9 Lesion Response for Enhancing Nontarget Lesions

Response	Definition
Complete Response (CR)	All enhancing nontarget lesions have disappeared completely.
Stable Disease (SD)	Enhancing lesions present, showing no definite growth from the visit where they were smallest.
Progressive Disease (PD)	Unequivocal progression of enhancing lesions (see below).
Non-evaluable (NE)	The sum of diameters cannot be meaningfully evaluated (for example, because of technical factors such as scan quality that obscure one or more target lesions).

Note on PD: The general approach is that nontarget lesions can be the basis for a determination of PD if it is clear, in the context of the entire scan, that there has been a sufficient increase in the tumor burden to demonstrate that treatment has failed.

New lesions are assessed in a binary yes/no fashion. If any new enhancing lesions are present, and the reviewer is confident that these are due to the presence of new malignancy, the response is “Yes,” otherwise, it is “No.” New lesions do not need to meet the size criteria for being considered measurable at baseline, but must, in the best judgment of the reviewer, be true tumor lesions rather than benign or incidental findings, or caused by some comorbidity. If the lesion is uncertain, it should be followed. If later scans reveal it to be a true lesion, the record can be retrospectively updated to show the new lesion at the time it was first identified.

The T2/FLAIR images are reviewed to determine whether there has been an unequivocal increase in tumor-related T2/FLAIR abnormality. This is performed with reference to the scan at which the T2/FLAIR abnormality is smallest (analogous to the nadir measurement for target lesions), and classified as increase, decreased, or unchanged. Because of the frequently

diffuse nature of the T2/FLAIR abnormality, it is performed at the scan level rather than by evaluation of discrete T2/FLAIR lesions. The reviewer must be confident that any recorded increase in T2/FLAIR abnormality is due to tumor rather than some alternative etiology (such as infection, infarction, demyelination, or other causes). If there is question about whether a change seen on T2/FLAIR represents progression, the participant continues to the next scheduled scan. If the subsequent scan confirms progression, the date of progression can be assigned retrospectively to the visit where the T2/FLAIR changes were first observed.

Target, nontarget, and new lesions are combined into a radiographic response (Table 10).

Table 10 Radiographic Response

Target Lesions	Enhancing Nontarget Lesions	FLAIR/T2 Lesions	New Lesions	Radiographic Response
CR	CR	No increase	No	CR
CR	SD or NE	No increase	No	PR
PR	CR, SD, or NE	No increase	No	PR
SD	CR, SD, or NE	No increase	No	SD
NE	CR, SD, or NE	No increase	No	NE
PD	Any	Any	Yes/No	PD
Any	PD	Any	Yes/No	PD
Any	Any	Any	Yes	PD
Any	Any	Increased	Yes/No	PD
NA ^a	CR	No increase	No	CR
NA ^a	SD	No increase	No	SD
NA ^a	NA ^a	No increase	No	NED ^b

^a NA – No lesions of this type were present at baseline.
^b NED (No evidence of disease) – No enhancing lesions were present at baseline, and no new lesions have appeared.

Pseudoprogression associated with radiotherapy

If new or increased enhancement is seen within 12 weeks of the completion of radiation therapy, but the participant is clinically stable and the investigator believes that the changes may be due to pseudoprogression, the participant may remain on treatment. A second scan should be performed, at least 6 weeks after the initial scan. If the enhancement continues to grow on this scan, progression is considered to have been confirmed at the time of the initial scan that showed increased enhancement. If the enhancement has stabilized or decreased on this second scan, the initial scan will be considered to have been confirmed as pseudoprogression. For endpoint assessment purposes, the initial scan will be equivalent to SD. On subsequent scans, in cases of confirmed pseudoprogression, all scans prior to the scan at which pseudoprogression was seen will be excluded when choosing the nadir value against which the size of enhancing lesions is compared.

If the new or increased enhancement occurs in an area that is known to be outside the irradiated area (outside the 80% isodose line), or if the participant shows clinical deterioration not caused by a comorbid condition or changes in steroid dosing, pseudoprogression will not be considered.

Overall Response

To make a final response determination, the radiographic response (Table 10) is combined with assessments of clinical status and of corticosteroid dose (Table 11).

Clinical status is measured using the Karnofsky Performance Scale. A participant's status is considered "stable" if there has been no definite decline in age-adjusted performance from their baseline state and is considered "worsening" if there has been definite decline in age-adjusted performance that is not attributable to a non-tumor-related cause. Examples of definite decline include a decline from 100 or 90 to 70 or less, a decline of at least 20 points from 80 or less, or a decline from any baseline to 50 or less, unless attributable to comorbid events or changes in corticosteroid dose.

Steroid dose is defined as the average daily dose since last visit. A dose of "none" means no corticosteroids above physiologic replacement dose. The dose is considered "stable" if it is unchanged or decreased from the visit at which the scans showed the smallest tumor burden. The dose is considered "increased" if it has increased from the visit at which the scans showed the smallest tumor burden.

For any overall response except PD, all the components of the definition (radiological, neurological, and steroid dose) must be present. However, either radiological progression or clinical deterioration (not attributable to a non-tumor-related cause) qualifies a participant for PD. However, an increase in steroid dose alone is not sufficient for an overall visit response of PD in the absence of clinical or radiological evidence of progression. A participant with a radiological response of SD, and without neurological evidence of progression, but requiring an increased dose of steroids, would still be considered SD overall at that visit (because increase in steroids alone is not PD). However, the participant will be reassessed at the next visit. If either radiological or neurological progression is documented at that next visit, the visit at which the increased dose was first observed would be retroactively reassessed as PD overall.

Table 11 Overall Response

Radiographic Response	Clinical Performance	Steroid Dose	Overall Response
CR	Stable	None	CR
CR	Stable	Stable or increased	PR
PR	Stable	Stable	PR
PR	Stable	Increased	SD
SD	Stable	Stable	SD
SD	Stable	Increased	SD or PD ^a
PD	Any	Any	PD
Any	Worsening	Any	PD
NE	Stable	Increased	NE or PD ^a
NED	Stable	Increased	NED or PD ^a

^a PD should not be based on an increase in steroid dose alone, unless confirmed by radiographic or clinical deterioration. If the steroid dose is increased while the radiographic assessment and clinical performance are stable, the participant should be re-evaluated at the next visit. If clinical or radiographic deterioration has occurred, progression can be retrospectively assigned at the visit when the steroid dose was increased.

Pseudoresponse and response confirmation

Pseudoresponse is a phenomenon observed in patients treated with antiangiogenic therapy and manifests as a transient decrease in tumor enhancement that does not reflect a true reduction in tumor burden. To avoid mistaken reporting of pseudoresponse as objective response, a visit response of PR or CR must be confirmed with a scan performed at least 4 weeks later that shows the same category of response or better. That is, a PR can be confirmed with a subsequent PR or CR, and a CR must be confirmed with a subsequent CR.

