 - b. Anticancer agents not known to be myelosuppressive (eg, not associated with reduced platelet or absolute neutrophil counts): ≥ 7 days after the last dose of agent.
 - c. Monoclonal antibodies: ≥ 21 days or 3 half-lives (whichever is shorter) of the antibody must have elapsed after the last dose of a monoclonal antibody (including checkpoint inhibitors; Appendix 14). Toxicity related to prior antibody therapy must be recovered to Grade ≤ 1 .
 - d. Corticosteroids: If used to modify immune AEs related to prior therapy, ≥ 14 days must have elapsed since last dose of corticosteroid. For reasons other than immune AEs, participants receiving corticosteroids who have not been on a stable or decreasing dose of corticosteroid for at least 7 days prior to enrollment are not eligible.
 - e. Hematopoietic growth factors: ≥ 14 days after the last dose of a long-acting growth factor (eg, NEULASTA[®]) or 7 days for short-acting growth factor. For agents that have known AEs occurring beyond 7 days after administration, this period must be extended beyond the time during which AEs are known to occur.
 - f. Interleukins, interferons, and cytokines (other than hematopoietic growth factors): ≥ 21 days after the completion of interleukins, interferons, or cytokines (other than hematopoietic growth factors).
 - g. Stem cell infusions (with or without total body irradiation):
 - Allogeneic (non-autologous) bone marrow or stem cell transplant, or any stem cell infusion including donor leukocytes infusion or boost infusion: ≥ 84 days after infusion and no evidence of graft versus host disease.
 - Autologous stem cell infusion including boost infusion: ≥ 42 days.
 - h. Cellular Therapy: ≥ 42 days after the completion of any type of cellular therapy (eg, modified T cells, natural killer cells, dendritic cells, etc).

- i. Radiotherapy (XRT)/External Beam Irradiation including Protons: ≥ 14 days after local XRT; ≥ 150 days after total body irradiation, craniospinal XRT, or if radiation to $\geq 50\%$ of the pelvis; ≥ 42 days if other substantial bone marrow radiation.
- j. Radiopharmaceutical therapy (eg, ^{131}I -MIBG): ≥ 42 days after systemically administered radiopharmaceutical therapy.
- k. VEGF/VEGFR-targeted therapies:
 - o Must not have received prior exposure to lenvatinib
 - o No more than 2 prior VEGF/VEGFR-targeted therapies

Demographics

11. Male or female ≥ 2 years to ≤ 21 years of age, on the day the main informed consent/assent is signed.

Male Participants

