9.6 Statistical Methods

9.6.1 Statistical Methods for Efficacy Analyses

This section describes the statistical methods that address the primary and secondary efficacy objectives. Methods related to exploratory objectives will be described in the sSAP.

Antitumor activity data will be analyzed by each tumor type. The data cutoff for the primary study analysis for a given tumor type will be determined by the study team, based on the review of data at each interim analysis and predetermined futility guidance.

Only those participants who have measurable disease present at baseline and have their disease re-evaluated at postbaseline visits will be considered evaluable for ORR. These participants will have their response classified according to RECIST 1.1 or RANO for participants with HGG.

Primary Efficacy Analysis

ORR: Objective responses will count only confirmed CR and PR at Week 16. Estimated ORR and its exact 95% CI using the method of Clopper and Pearson will be presented.

Secondary Efficacy Analyses

The BOR will be provided with the descriptive statistics. The ORR, DCR, and CBR will be provided with exact 95% CIs using the method of Clopper and Pearson, and the DOR will be analyzed for responders using Kaplan-Meier approach.

The secondary endpoint of PFS will be analyzed using Kaplan-Meier product-limit estimates. Median PFS and the cumulative probability of PFS at 4, 6, 12, and 24 months will be presented with 2-sided, 95% CIs when an adequate number of at-risk participants at those time points warrant the estimate. The cumulative PFS probabilities will be plotted over time as appropriate.

A summary of the primary analysis strategy for the key efficacy endpoints is provided in [Table 5](#).

Table 5 Table Analysis Strategy for Key Efficacy Variables

Endpoint/Variable	Statistical Method	Analysis Population	Missing Data Approach
Primary Analyses – Within tumor type			
ORR (RECIST 1.1 or RANO for HGG) at Week 16	Summary statistics using Clopper and Pearson method	EAS	Participants in EAS with missing data are considered nonresponders.
Secondary Analyses – Within tumor type			
ORR	Summary statistics using Clopper and Pearson method	EAS	Participants in EAS with missing data are considered nonresponders.
BOR	Summary statistics using Clopper and Pearson method	EAS	Missing observation in EAS population are counted as nonresponders.

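### RANO Table 11 drops a radiographic PR on an increased steroid dose to SD but keeps a radiographic CR on an increased dose as a countable PR, so the HGG primary ORR rests on an inconsistent scoring rule

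*Combined protocol and SAP*

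**What the plan says.** Appendix 8 (Section 10.8) derives the HGG visit response in two steps. Table 10 gives a radiographic response. Table 11 then combines it with clinical performance and steroid dose.

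With stable clinical performance, row 2 of Table 11 scores a radiographic CR as overall PR when the steroid dose is "Stable or increased". Row 3 scores a radiographic PR on a stable dose as PR. Row 4 reads "PR Stable Increased SD".

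The text before the table states: "For any overall response except PD, all the components of the definition (radiological, neurological, and steroid dose) must be present". The reference for a dose change is the visit of smallest tumor burden, not baseline: "The dose is considered 'increased' if it has increased from the visit at which the scans showed the smallest tumor burden".

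Confirmation needs a scan at least 4 weeks later, with the purpose "To avoid mistaken reporting of pseudoresponse as objective response". The rule is by category: "That is, a PR can be confirmed with a subsequent PR or CR, and a CR must be confirmed with a subsequent CR".

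Section 9.6.1 sets the primary analysis: "Objective responses will count only confirmed CR and PR at Week 16". Section 4.1 makes the site assessment the basis for the primary endpoint.

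**The concern.** The same change in steroid dose is treated in two ways. It removes response status from a partial shrinkage, but has no effect on the label when enhancement has disappeared. Since overall PR counts toward ORR and SD does not, row 2 is the only place in the CR, PR and SD part of the table where a visit on an increased dose still counts.

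This matters because HGG response is read largely on contrast enhancement. Appendix 8 itself warns that antiangiogenic treatment can reduce enhancement without a true reduction in tumor. Requiring a stable steroid dose guards against a related misreading, and row 2 waives that requirement for one radiographic category.

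Steroid changes are possible on study. Section 5.1 excludes only some users at entry ("participants receiving corticosteroids who have not been on a stable or decreasing dose of corticosteroid for at least 7 days prior to enrollment are not" admitted), so those on a stable or falling dose may enrol. Section 6.5 limits systemic steroids on treatment to premedication and short-term care of acute conditions, but does not rule them out.

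At stake are the HGG ORR at Week 16, its exact interval, the overall ORR, and who enters the DOR analysis. With about nine participants, a single reclassified case is visible in each.

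**Working it through.** The plan states no figure for this point, so there is none to reproduce. The check is an enumeration of the table, then a sizing.

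**Step 1. Table 11 with stable clinical performance**

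| Radiographic | Steroid dose | Overall | Counts in ORR if confirmed |
|---|---|---|---|
| CR | None | CR | yes |
| CR | Stable | PR | yes |
| CR | Increased | PR | yes |
| PR | Stable | PR | yes |
| PR | Increased | SD | no |
| SD | Stable | SD | no |
| SD | Increased | SD or PD | no |

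For a radiographic PR, moving from a stable to an increased dose changes PR to SD. For a radiographic CR, the same move changes PR to PR. Of the three combinations with an increased dose, only the CR one counts.

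**Step 2. Against the text.** Rows 3 and 4 show that the steroid component of an overall PR is a stable dose, because an increased dose fails it. The sentence above the table says the component must be present. Row 2 awards PR without it.

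**Step 3. Route into the primary endpoint.** This depends on whether the reference visit for an increase can be the current visit, which the text leaves open.

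- If only earlier visits count, a first CR on a raised dose is increased and scores PR by row 2. A second such visit at least 4 weeks later also scores PR. That is a confirmed response.
- If the current visit can be the reference, the dose at a first CR cannot be increased against itself. It is labelled stable even if it has risen since baseline, and scores PR. The increased part of row 2 then acts only at a later CR visit, where it can confirm the response.

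The confirmation rule adds no steroid condition. Section 9.6.1 and Table 5 contain no steroid rule and no sensitivity analysis. Sections 9.7.2 and 9.9 are redacted, so they cannot be checked.

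**Step 4. Size.** Assume 9 evaluable HGG participants (the planned minimum, Section 4.1) and use the plan's Clopper-Pearson method.

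- 0 of 9: upper limit = 1 − 0.025^(1/9) = 0.336. ORR 0% (0 to 33.6).
- 1 of 9: lower limit = 1 − 0.975^(1/9) = 0.003. The upper limit p solves (1 − p)^9 + 9p(1 − p)^8 = 0.025, giving p = 0.482. ORR 11.1% (0.3 to 48.2).

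**Step 5. How likely is one case?** The documents give no rate. If each participant had probability q of such a confirmed response, the chance of at least one in 9 is 1 − (1 − q)^9. For assumed q of 0.5%, 1%, 2% and 5%, this is about 4%, 9%, 17% and 37%. These values of q are illustrative only.

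**The case against.** The best defence is that the table applies a consistent one-step downgrade: CR to PR, PR to SD, SD to possibly PD. It does not fit. A CR on a stable dose is already PR, so in the CR rows the increase itself costs nothing. Even under that reading, a visit on an increased dose still enters ORR.

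A second defence is that the components sentence does not say the dose must be stable, and the same paragraph keeps SD on an increased dose as SD. This stands in part. The sentence alone does not decide the matter; the conflict appears only when it is read with rows 3 and 4. Row 2 might be a deliberate separate route to PR, but nothing says so. The criteria follow a cited publication that is not available here, so no claim is made about departure from it.

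A reader might infer that steroid-driven responses are being counted. The documents do not support that. An increased dose does not establish cause. If a CR first appears on a stable dose and the dose rises only before the confirmatory scan, the disappearance preceded the rise. A reader might also infer that the pseudoresponse safeguard is lost. It is not: confirmation still applies, and Table 10 also requires all enhancing lesions gone, no T2/FLAIR increase and no new lesions.

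Finally, a reader might infer that one such case carries the cohort past the rule that stops enrollment at 0 of 9. Section 4.4 reports that HGG was not expanded because futility was concluded in the companion study, so that consequence is only illustrative.

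**Conclusion.** The concern holds as an internal inconsistency in Table 11 that reaches the HGG primary endpoint. A radiographic CR visit on an increased steroid dose can establish or confirm an objective response, while a radiographic PR visit on the same increase cannot.

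The direction of any error in ORR would be upward, but its existence and amount are unknown. Cases should be rare, given the radiographic requirements and the limits on steroid use in Section 6.5. The effect is confined to the HGG estimates and the DOR responder set. The change of one responder sized above assumes exactly 9 evaluable participants and that the affected participant is the only responder; the two intervals overlap widely.

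The extent also depends on the undefined reference visit. If it can be the current visit, some dose rises since baseline are labelled stable, and correcting row 2 alone would not reach them. The correction is worth making because it is cheap and the cohort is small.

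**What to change.** 1. Split row 2 of Table 11. CR with stable performance and a stable dose remains PR. CR with stable performance and an increased dose becomes SD, as row 4 already does for a radiographic PR. This brings the row into line with the components sentence.
2. State whether the smallest-burden visit that defines an increase can be the current visit, and which visit applies when several tie, as successive CR visits would.
3. If the sponsor intends row 2 as written, keep it, say why, and add a sensitivity HGG ORR that treats visits scored CR or PR on an increased steroid dose as non-response.
4. Check recorded HGG visit responses against the clarified rule before the primary analysis, and report ORR with its exact interval under both scorings.

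The cost is one table row, one or two sentences and a check of a few visits, using the steroid doses that RANO scoring already requires. The downside is that a true response could be downgraded when steroids were raised for an unrelated acute condition. Rescoring open-label data also invites questions about motive. Reporting both scorings answers both points. The change concerns response scoring only and proposes no rule on steroid use. Treatment continues until progression (Section 4.1), so rescoring a visit from PR to SD would not in itself stop it.
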